As of 29 September 2021, data cut, subjects (100.0%) receiving monotherapy in Part A2 (ie, cohort 30) had treatment-emergent events. Grade ≥ 3 adverse events were reported in subjects (35.3%). Serious adverse events were reported in subjects (52.9%). No adverse events were fatal or led to discontinuation of tarlatamab. Adverse

Protocol Number: 20200439

Date: 05 June 2024 Page 29 of 176

events by preferred term reported for ≥ 20.0% of subjects were CRS (subjects [76.5%]); dysgeusia and pyrexia (each subjects [47.1%]); decreased appetite, headache, and vomiting (each subjects [29.4%]); and arthralgia, fatigue, and nausea (each subjects [23.5%]).

Among subjects who received tarlatamab in Part A2, CRS was grade ≥ 2 in subjects (11.8%); no grade ≥ 3 events were reported. In subjects (41.2%), CRS was reported as a serious adverse event. No CRS (AMQN) adverse events were fatal or led to discontinuation of tarlatamab.

[figure not shown]
Neutropenia was grade ≥ 2 in subjects (23.5%) and grade ≥ 3 in subjects (11.8%). Neutropenia was reported as a serious adverse event in subject (5.9%). No neutropenia adverse events were fatal or led to discontinuation of tarlatamab.

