9.1 General Considerations

Descriptive statistics will be provided for selected demographics, safety, pharmacokinetic, efficacy data by dose, dose schedule, and time as appropriate. Descriptive statistics on continuous data will include means, medians, standard deviations and ranges, while categorical data will be summarized using frequency counts and percentages. Graphical summaries of the data may also be presented. Confidence intervals (CI) for proportions will be estimated using an exact method proposed by Clopper-Pearson (Clopper and Pearson, 1934). Kaplan-Meier methods will be used to estimate the median and percentiles for time to event endpoints with CI calculated using the Brookmeyer and Crowley (Brookmeyer and Crowley, 1982) method. Kaplan-Meier methods will be used to estimate landmarks for time to event endpoints (eg, 1-year OS) with the Greenwood formula (Kalbfleisch and Prentice, 1980) used to estimate the standard error used in CI calculation.

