For the list of EOIs mentioned above, the subject incidence of treatment-emergent adverse events of interest (standardized MedDRA queries and/or Amgen Medical Queries), grade ≥ 2 , grade ≥ 3 , grade ≥ 4 , serious, fatal, and events leading to interruption, reduction or discontinuation of IP will be summarized.

The subject incidence of above treatment-emergent EOIs will be tabulated by preferred term. CRS will be graded according to Lee et al, 2014.

The summaries of time to onset of EOI from first dose of IP (days), which comes earlier, time to onset of EOI after each dose from last prior dose of IP (days), which comes later(days), time to onset of CRS from first dose of tarlatamab (hours), time to onset of CRS from each last prior tarlatamab dose (hours), and duration of treatment-emergent

Date: 27 Sep 2024 Page 39 of 51

EOI will be provided. Additionally, summaries of time to onset and duration of EOI will be provided for grade 2 or higher and grade 3 or higher EOIs respectively.

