Appendix A. Date Imputation Rules

Imputation rules for partial or Missing Dates for Adverse Events and concomitant Medication are detailed below. Date of on-study anti-cancer therapy will be imputed using the same rule when only the day is missing (no imputation when month or year is missing).

Imputation Rules for Partial or Missing Start Dates

		Stop Date						
		Complete: yyyymmdd		Partial: yyyymm		Partial: yyyy		
Start Date		< 1 st dose	≥ 1 st dose	< 1 st dose yyyymm	≥ 1 st dose yyyymm	< 1 st dose yyyy	≥ 1 st dose yyyy	missing
Partial: yyyymm	= 1st dose yyyymm	2	1	2	1	n/a	1	1
	≠ 1 st dose yyyymm		2		2	2	2	2
Partial:	= 1 st dose yyyy	3	1	3	1	n/a	1	1
	≠ 1 st dose yyyy		3		3	3	3	3
Missing		4	1	4	1	4	1	1

¹⁼Impute the date of first dose; 2=Impute the first of the month; 3=Impute January 1 of the year; 4=Impute January 1 of the stop year

Note: For subjects who were never treated (first dose date is missing), partial start dates will be set to the first day of the partial month or first day of year if month is also missing.

Note: If the start date imputation leads to a start date that is after the stop date, then do not impute the start date.

1. Imputation rules for partial or missing stop dates:

Initial imputation

- If the month and year are present, impute the last day of that month.
- If only the year is present, impute December 31 of that year.
- If the stop date is entirely missing, assume the event or medication is ongoing.

If the imputed stop date is before the start date, set stop date to missing.

If the imputed stop date is after the death date, impute as death date.

Date: 27 Sep 2024 Page 45 of 51

2. Imputation rules for partial or missing death dates:

- If death year and month are available but day is missing:
 - If mmyyyy for last contact date = mmyyyy for death date, set death date to the day after the last contact date.
 - If mmyyyy for last contact date < mmyyyy for death date, set death date to the first day of the death month.
 - If mmyyyy for last contact date > mmyyyy for death date, data error and do not impute.
- If both month and day are missing for death date or a death date is totally missing, do not impute.

Note that the last contact date refers to the last contact (i.e. a visit or an assessment) with patient instead of family members. Last contact date would be derived from the latest patient visit/assessment date.

Date: 27 Sep 2024 Page 46 of 51

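### SAP 9.6.2 plans duration summaries for events of interest but gives no rule for events still open, so dropping or truncating those events would bias the reported duration downward

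*SAP*

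**What the plan says.** SAP 9.6.2 plans summaries of several EOI timings, including "time to onset of CRS from each last prior tarlatamab dose (hours), and duration of treatment-emergent" EOI. It adds that "summaries of time to onset and duration of EOI will be provided for grade 2 or higher and grade 3 or higher EOIs respectively". It does not define duration, name an estimator, or say how an unresolved event enters the summary.

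Three other places bear on the handling:

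- **SAP 9.1:** "Descriptive statistics on continuous data will include means, medians, standard deviations and ranges". Kaplan-Meier is kept for time-to-event endpoints. EOI duration is not among the endpoints in SAP 2.1.
- **SAP Appendix A:** "If the stop date is entirely missing, assume the event or medication is ongoing". No end date follows from this. Partial stop dates are completed late: "If the month and year are present, impute the last day of that month", and "If only the year is present, impute December 31 of that year". The limit at death, "If the imputed stop date is after the death date, impute as death date", covers imputed stop dates only. An event with an entirely missing stop date in a subject who dies still has no end date.
- **Protocol Appendix 4 (11.4):** a resolution date is recorded only for events that resolved. The outcome of every event is recorded.

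Elsewhere the SAP does state how open observations are handled. SAP section 5 and Appendix C give censoring rules for duration of response, duration of disease control, progression-free survival and overall survival.

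**The concern.** Duration is a length-dependent quantity observed over a limited time. The longer an event lasts, the more likely it is to be open when the data are cut. A summary that needs a stop date keeps the short events and loses a disproportionate share of the long ones. Using the cutoff as the stop date keeps every event but shortens the open ones. Both errors run in the same direction.

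The primary objective is safety and tolerability. How long neurological events, immune effector cell-associated neurotoxicity syndrome (ICANS) and neutropenia last is part of that answer. In a table restricted to resolved events, every event shown has ended, so the table alone cannot show how often events fail to resolve. The gap applies to the any-grade summary and to the grade 2 or higher and grade 3 or higher summaries alike.

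**Working it through.** **The plan's own figure.** There is none to reproduce. The documents give no EOI durations and no share unresolved.

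**What the text leads to.** EOI duration is a continuous quantity and not a listed endpoint, so the SAP 9.1 default is descriptive statistics. Duration needs a start and a stop. Appendix A supplies no stop for an ongoing event. SAP Table 7 shows the usual handling of such a variable: time to response is summarised with plain statistics on the non-missing n.

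**Whether open events are likely.** Protocol 8.4.9.3 follows adverse events to resolution, but follow-up may also end at stabilisation, another explanation, or loss to follow-up. SAP 7.2 sets the primary analysis once each subject has 6 months on study or has withdrawn. Some events can therefore be open at the cutoff or at death.

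**Direction and size, exponential case.** Assume exponential durations with rate λ, a time from onset to end of observation uniform on (0, c), and x = λc. An event of length t is open with probability t/c (up to 1), which rises with t.

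- Share unresolved: f = (1 − e^(−x))/x. For f = 0.20, x = 4.965: 0.993/4.965 = 0.200.
- Share of all events that resolve by u (in units of 1/λ): (1 − e^(−u)) − [1 − e^(−u)(1 + u)]/x. The resolved-only median is where this equals half of 0.80. At u = 0.547: 0.421 − 0.021 = 0.400.
- True median: ln 2 = 0.693. Ratio: 0.547/0.693 = 0.79.
- Cutoff used as stop date: solve e^(−u)(1 − u/x) = 0.5. At u = 0.571: 0.565 × 0.885 = 0.500. Ratio: 0.571/0.693 = 0.82.
- For f = 0.05, x = 20.0. The resolved-only median is at u = 0.658, ratio 0.95. With the cutoff as stop date, u = 0.660, ratio 0.95.

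**Other shapes.** A simulation of 200,000 events per shape, with the true median set to 1.00 and uniform censoring tuned to each share unresolved, gave these medians as a fraction of the true median:

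| Unresolved | Resolved only: exponential | Resolved only: Weibull 0.7 | Resolved only: Weibull 1.5 | Cutoff as stop (range over shapes) | Kaplan-Meier |
|---|---|---|---|---|---|
| 2% | 0.97 | 0.96 | 0.99 | 0.97–0.98 | 0.99–1.00 |
| 5% | 0.94 | 0.91 | 0.97 | 0.95–0.96 | 1.00 |
| 10% | 0.89 | 0.83 | 0.94 | 0.90–0.92 | 0.99–1.00 |
| 20% | 0.79 | 0.67 | 0.88 | 0.82–0.84 | 1.00 |
| 30% | 0.68 | 0.54 | 0.81 | 0.73–0.77 | 1.00 |
| 40% | 0.57 | 0.42 | 0.73 | 0.64–0.70 | 1.00 |

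The exponential column agrees with the closed form to within simulation error. Kaplan-Meier with open events censored recovers the true median throughout, given that censoring is independent of duration in this set-up.

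**The case against.** The strongest reply is that the SAP is silent and not wrong. It never says that open events are excluded. The Kaplan-Meier sentence in SAP 9.1 could be read to cover duration, and SAP section 12 leaves the list of outputs to a Program Index that is not part of these documents. This stands: exclusion is inferred from the defaults. Even on the sponsor's best reading, though, no censoring date is given for EOI duration.

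Other points that stand:

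- Open does not mean long. An event that began just before the cutoff is also open. The supportable statement is that open events are disproportionately long.
- Follow-up under Protocol 8.4.9.3 can run past the reporting window in 8.4.9.1.1. Enrollment ended in January 2023 (Protocol 4.1) and the SAP is dated 27 September 2024, so many early-cycle events will have had long follow-up.
- Protocol 2.2.2.3 describes CRS with tarlatamab monotherapy as reversible and mostly following the first two doses, so few CRS events should be open.
- Late imputation of partial stop dates lengthens some resolved events. It does not bring open events back.
- Recorded outcomes would show non-resolution, if they were tabulated next to duration.
- No hypothesis is tested, and no dose or stopping rule uses EOI duration.
- SAP 9.6.2 takes onset after each dose, so one subject can contribute several events. Death in relapsed small cell lung cancer may not be independent of an open event. Kaplan-Meier needs a stated position on both.

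A reader might also infer persistence from the high monotherapy incidences of some symptoms in Protocol 2.2.2.3. Incidence says nothing about duration, so that inference is not used here.

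**Conclusion.** The point holds conditionally. SAP 9.6.2 plans EOI duration with no rule for open events. Under the defaults in SAP 9.1 and Appendix A, those events have no computable duration. If they are dropped, or cut at the cutoff and averaged, duration is understated.

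A reader might go further and infer that the durations this trial reports are too short. The documents do not support that. They do not say that open events will be dropped, and they do not give the share unresolved. The ranges of 0.91 to 0.97 at 5% unresolved and 0.67 to 0.88 at 20% rest on assumed exponential or Weibull durations and uniform censoring. They illustrate sensitivity and do not predict this trial's result. The effect is probably small for CRS and could be larger for an EOI with many unresolved events.

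This is a minor improvement to a descriptive safety analysis. It is more than a missing definition, because both simple handlings are biased and the SAP already contains a method that avoids the bias.

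**What to change.** In SAP 9.6.2:

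1. Define EOI duration, with its start and stop.
2. For each EOI, report the number and percent of events unresolved, counting separately those open at death.
3. Estimate the median and quartiles by Kaplan-Meier, with the stop date as the event. Censor unresolved events at the earliest of death, last follow-up of that event, and data cutoff. Do not censor at the end of the adverse event reporting window, since Protocol 8.4.9.3 can follow events beyond it.
4. State that censoring at death assumes death is non-informative.
5. Use one event per subject, or note that the confidence intervals ignore within-subject correlation.
6. Label any plain summary that is kept as covering resolved events only.

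The cost is SAP wording and some output programming. Kaplan-Meier is already in the SAP and no new data are needed. Reported durations may come out longer, and an upper quartile may not be reached where many events are open.

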9.6.3 Laboratory Test Results

The analyses of safety laboratory endpoints will include summary statistics at selected time points by cohort. Shifts in grades of safety laboratory values between the baseline and the worst on-study value will be tabulated by cohort.

Summaries of the absolute value and/or changes from baseline at each scheduled assessment will be provided for selected laboratory parameters of interest.

Shift tables indicating the change between the baseline and the maximum post dose CTCAE grades for an increased value, and the maximum post dose grade for a decreased value will be provided for selected laboratory parameters of interest.

Unscheduled assessments will be included in the shift tables.

Potential Hy's law cases will be listed and may also be summarized by cohort. Hy's law cases will have the following three components: 1) ALT or AST > 3 X ULN, 2) ALP < 2 X ULN and 3) TB >2 X ULN, on any day. A listing of AST, ALT and Total Bilirubin values at each time point will be produced for the subjects suspected of Hy's law case.

9.6.4 Vital Signs

The analyses of vital signs will include summary statistics at selected time points by treatment group. Shifts in vital sign values between the baseline and the worst on-study value will be tabulated by treatment group.

The vital sign includes systolic/diastolic blood pressure, heart rate, respiratory rate, temperature and pulse oximetry and will be summarized using descriptive statistics. The summary statistics will be presented for baseline and scheduled post-baseline visits. In addition, summaries for changes from baseline over time may be summarized, provided the scope and size of changes is feasible.

Shifts in scores for ECOG performance status scores between the baseline and each scheduled / assessed time point will be tabulated. ECOG performance status scores will be summarized for each cohort at the relevant time points.

9.6.5 Physical Measurements

The analyses of physical measurements will include summary statistics at baseline by treatment group. Depending on the size and scope of the changes, the summaries of

Date: 27 Sep 2024 Page 40 of 51

changes from baseline over time may be provided. These summaries will also include the unscheduled visits.

9.6.6 Electrocardiogram

Summaries over time and/or changes from baseline over time will be provided for available ECG parameters.

9.6.8 Exposure to Investigational Product

Subject exposure to investigational product and combination therapy will be summarized using descriptive statistics. The number of doses per subject, cumulative dose (mg), relative dose intensity (%), treatment duration (weeks) will be summarized. The number and percent of subjects with dose modifications (eg, dose reductions, dose interruptions) and reason for modification will also be summarized. Subject-level data may be provided instead of the summary if the subject incidence is low or single dose is given.

9.6.9 Exposure to Non-investigational Product

Not applicable for this study.

9.6.10 Exposure to Other Protocol-required Therapy

Descriptive statistics will be produced to describe the exposure to other protocol specified therapy (i.e., corticosteroids such as dexamethasone and tocilizumab).

Descriptive statistics of the number of doses per subject, cumulative dose (mg), relative dose intensity (%), treatment duration (weeks).

9.6.11 Exposure to Concomitant Medication

Number and proportion of subjects receiving therapies of interest may be summarized by preferred term for each cohort as coded by the World Health Organization, 2018. A subject listing of all prior and concomitant medications may be provided.

Date: 27 Sep 2024 Page 41 of 51

9.7 Other Analyses

9.7.1 Analyses of Pharmacokinetic or Pharmacokinetic/Pharmacodynamic Endpoints

[figure not shown]
Pharmacokinetic parameters will be determined from the time concentration profile using standard non-compartmental approaches and considering the profile over the complete sampling interval.

9.7.2 Analyses of Clinical Outcome Assessments

Not applicable for this study.

Appendix A. Date Imputation Rules

Imputation rules for partial or Missing Dates for Adverse Events and concomitant Medication are detailed below. Date of on-study anti-cancer therapy will be imputed using the same rule when only the day is missing (no imputation when month or year is missing).

Imputation Rules for Partial or Missing Start Dates

		Stop Date						
		Complete: yyyymmdd		Partial: yyyymm		Partial: yyyy		
Start Date		< 1 st dose	≥ 1 st dose	< 1 st dose yyyymm	≥ 1 st dose yyyymm	< 1 st dose yyyy	≥ 1 st dose yyyy	missing
Partial: yyyymm	= 1st dose yyyymm	2	1	2	1	n/a	1	1
	≠ 1 st dose yyyymm		2		2	2	2	2
Partial:	= 1 st dose yyyy	3	1	3	1	n/a	1	1
	≠ 1 st dose yyyy		3		3	3	3	3
Missing		4	1	4	1	4	1	1

¹⁼Impute the date of first dose; 2=Impute the first of the month; 3=Impute January 1 of the year; 4=Impute January 1 of the stop year

Note: For subjects who were never treated (first dose date is missing), partial start dates will be set to the first day of the partial month or first day of year if month is also missing.

Note: If the start date imputation leads to a start date that is after the stop date, then do not impute the start date.

1. Imputation rules for partial or missing stop dates:

Initial imputation

- If the month and year are present, impute the last day of that month.
- If only the year is present, impute December 31 of that year.
- If the stop date is entirely missing, assume the event or medication is ongoing.

If the imputed stop date is before the start date, set stop date to missing.

If the imputed stop date is after the death date, impute as death date.

Date: 27 Sep 2024 Page 45 of 51

2. Imputation rules for partial or missing death dates:

- If death year and month are available but day is missing:
 - If mmyyyy for last contact date = mmyyyy for death date, set death date to the day after the last contact date.
 - If mmyyyy for last contact date < mmyyyy for death date, set death date to the first day of the death month.
 - If mmyyyy for last contact date > mmyyyy for death date, data error and do not impute.
- If both month and day are missing for death date or a death date is totally missing, do not impute.

Note that the last contact date refers to the last contact (i.e. a visit or an assessment) with patient instead of family members. Last contact date would be derived from the latest patient visit/assessment date.

Date: 27 Sep 2024 Page 46 of 51

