Half-Life (t_{1/2})

The time required for the observed concentration of a drug to be reduced by one-half.

Investigational Product

The term 'investigational product' is used in reference to tarlatamab and AMG 404.

Last Investigational Product Dose Date

The last IP date for each subject is defined as the latest date IP administered.

Last Known Alive Date:

Last known alive date is the latest date of the following dates before death date:

- Date of Enrollment on Subject Enrollment form
- Date First Taken, Date Last Taken on Concomitant Medications form, Other
 Protocol Required Therapy form, and Anti-Cancer Therapies (Subsequent) form
- Date Performed on ECOG Performance Status, Vital Signs, MUGA scan or Echocardiogram, Electrocardiogram and Mini Mental Status Examination forms
- Admission Date, Discharge Date on Hospitalizations form, Date of Examination on Physical Measurement form
- Date Collected on all lab forms (e.g., Pregnancy Test (Local Lab), Chemistry (Local Lab), Hematology (Local Lab), Coagulation (Local Lab), Urinalysis (Local Lab)) and in central lab data
- Start Date, Stop Date on Investigational Product Administration forms.
- Start date and Stop date on Cytokine Release Syndrome form

Date: 27 Sep 2024 Page 25 of 51

Date subject ended on End of Investigational Product Administration (AMG 757),
 End of Investigational Product Administration (AMG 404), and End of Study, End of Safety Follow-up, and End of Radiographic Follow-Up forms where the primary reason is not death or lost to follow-up.

- Date Started and Date Ended but not Resulted in Death on Events form.
- Subject Status Date if status is Alive on Survival Status form
- Date Performed on 'CT or MRI', 'Neurological Evaluation', 'Writing Test' forms
- Date of Imaging for Index Lesions, New Lesions and Non-Index Lesions
- Date Scan Performed for Tumor Response Assessment
- Date performed for Procedure, Transfusions, Liver Biopsy Results, Liver Imaging Results forms
- Date Consent Signed, Date Consent Withdrawn from Additional Consents/Withdrawal of Consent form

If death happened, then last known alive date is death date minus 1.

Death date sources eCRF forms:

- End of study, End of Radiographic Follow-Up and End of Safety Follow-up
- Events
- End of Investigational Product Administration (AMG 757), End of Investigational Product Administration (AMG 404)
- Survival Status

Long Term Follow-Up

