Long term follow-up will be conducted every 3 months (±2 weeks) up to 1 year from the first dose of tarlatamab for all subjects who have not withdrawn consent by clinic visit, telephone, or chart review to assess for survival and/or the commencement of subsequent cancer therapy only.

For subjects who discontinued treatment for any reason other than confirmed progressive disease, every effort should be made to perform radiographic imaging (computed tomography [CT]/MRI) of the chest, abdomen, pelvis, and all other known sites of disease every 3 months until documentation of confirmed disease progression per modified RECIST 1.1, clinical progression, start of new anticancer therapy, or up to 12 months after the first dose of tarlatamab, whichever occurs first.

Modified Toxicity Probability Interval (mTPI)

Date: 27 Sep 2024 Page 26 of 51

The modified toxicity probability interval for target dose-limiting toxicity (DLT) probability of 30% is defined as equivalence toxicity of interval as (25%, 33%) and probability of overdosing of 95% with Beta (1,1) as the prior distribution.

Objective response (OR)

Objective Response is defined as a best overall response of either Complete Response (CR) or Partial Response (PR) per modified RECIST 1.1. Radiographic response

(Complete Response, Partial Response) requires confirmation by a repeat, consecutive scan at least 4 weeks after the first documentation of response.

Objective Response Rate (ORR)

ORR is defined as the incidence of a BOR of a confirmed CR or PR while on study as defined by modified RECIST 1.1. All subjects that do not meet the criteria for objective response by the analysis cut-off date will be considered as non-responders.

Objective Response Rate (ORR) based on Unconfirmed Response

ORR based on unconfirmed response is defined as the incidence of a BOR of CR or PR which do not require confirmation while on study as defined by modified RECIST 1.1. Only unconfirmed response awaiting confirmatory scan is considered in the ORR based on unconfirmed response.

Overall Survival (OS)

OS (in Months) is defined as the interval from the earlier date of first dose of tarlatamab or AMG 404 to the event of death due to any cause. Subjects still alive will be censored at the date last known to be alive. If the date last known to be alive is after the date that triggers the analysis (ie, the data cutoff date), the subject will be censored at the analysis trigger date.

Percent change from Baseline

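### Imputed death dates are not checked against the SAP's own alive dates, and a known death with only a year or no date has no stated OS treatment

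*SAP*

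**What the plan says.** SAP Section 8.3 sends incomplete death dates to Appendix A. Item 2 there has three branches when the month and year of death are known.

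- Last contact in the death month: "set death date to the day after the last contact date".
- Last contact in an earlier month: "If mmyyyy for last contact date < mmyyyy for death date, set death date to the first day of the death month".
- Last contact in a later month: treated as a data error and left unimputed.

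For less complete dates, "If both month and day are missing for death date or a death date is totally missing, do not impute".

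The anchor is narrow: "Note that the last contact date refers to the last contact (i.e. a visit or an assessment) with patient instead of family members", and "Last contact date would be derived from the latest patient visit/assessment date".

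SAP Section 5 (Definitions) builds a separate last known alive date from many more sources. These include concomitant medication, subsequent anti-cancer therapy, hospital admission and discharge, and "Subject Status Date if status is Alive on Survival Status form". Only dates before the death date count, and "If death happened, then last known alive date is death date minus 1".

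For OS, the same section says "Subjects still alive will be censored at the date last known to be alive". It gives no rule for a subject known to be dead without a usable date.

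**The concern.** One endpoint uses two different sets of dates. A living subject is censored using all alive sources, while a death with a missing day is placed using visits and assessments only. The two can diverge in long-term follow-up, where Protocol Section 8.1.4 allows survival to be assessed by clinic visit, telephone or chart review. A subject can therefore have a documented alive date later than the last visit, and nothing in item 2 makes the imputed death respect it.

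The omission stands out because Appendix A does check order elsewhere. An adverse-event or medication start date imputed after the stop date is not used, and an imputed stop date after death is pulled back to the death date.

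At stake are OS, PFS for subjects whose event is death, and the 6-month landmarks named in Protocol Section 9.4.2.2. The undated-death gap is a different problem. Someone will have to decide at analysis whether such a subject is censored, dropped or counted, and the SAP does not say which.

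**Working it through.** The documents give no figure to reproduce here, so the check applies the rules as written to assumed dates.

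**Inputs.** The item 2 branches and the last-contact definition come from Appendix A, and the alive sources from SAP Section 5. The month conversion is the SAP's DOR convention, (date − first dose + 1) × 12 / 365.25, applied to OS. First dose is assumed to be 5 September 2022. In cases A and B the subject is documented alive on 20 March 2023 by a source that is not a visit or assessment (for example chart review or hospital discharge) and died in March 2023, day unknown.

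| Case | Last visit | Imputed under item 2 | Days before the alive date | OS under item 2 | OS if anchored on the alive date (21 March) |
|---|---|---|---|---|---|
| A, visit in death month | 3 March 2023 | 4 March 2023 | 16 | 181 × 12 / 365.25 = 5.95 months | 198 × 12 / 365.25 = 6.51 months |
| B, visit in earlier month | 15 January 2023 | 1 March 2023 | 19 | 178 × 12 / 365.25 = 5.85 months | 6.51 months |

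The OS differences are 0.56 month (A) and 0.66 month (B). In both cases the subject counts as dead by 6 months under item 2 and alive at 6 months under the other anchor. The first-dose date was chosen so that this crossing is visible; it will not happen for every partial date.

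**Control.** If the last visit on 3 March is also the last alive date, both anchors give 4 March and nothing changes.

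**Upper limit for a month-known death.** Take a last visit in an earlier month and an alive date at the end of a 31-day month. Item 2 gives the 1st and the alive date is the 31st: 30 days, or 30 × 12 / 365.25 = 0.99 month.

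**A missed error.** Suppose the last visit is 15 January, chart review shows the subject alive on 5 April, and death is recorded in March. Item 2 compares January with March and imputes 1 March. The data-error branch never sees the April date.

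**Undated death.** With year only, item 2 returns no date. The OS event has no time, and the censoring rule does not apply because the subject is not alive.

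For the effect of the choice left open, assume 40% mortality by 6 months, no other censoring, one death affected, and n = 10 or 20 (the illustrative expansion sizes in Protocol Section 9.2). True 6-month OS is 60.0%.

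- n = 10: censoring the subject gives 6/9 = 66.7% to 7/10 = 70.0%, depending on when; dropping the subject gives 66.7%.
- n = 20: censoring gives 12/19 = 63.2% to 13/20 = 65.0%; dropping gives 63.2%.

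These figures show what one such subject could do if censored or dropped. They are not a prediction that any will occur.

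**The case against.** The strongest reply has four parts.

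**Telephone calls.** A reader might infer that item 2 ignores every telephone survival check. The text does not go that far. It excludes contact with family members, and a call with the patient can be read as an assessment with the patient. On that reading a known-alive call moves the anchor and the conflict disappears. This stands and narrows the point. Chart review, hospital, medication and subsequent-therapy dates are still not clearly contacts with the patient, and Section 5 counts them as evidence of life.

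**Undated deaths.** A reader might also infer that the SAP censors undated deaths as if alive and so biases OS upward. It does not say so. Its censoring sentence is limited to living subjects, so the treatment is undefined and the direction of any bias depends on what is later chosen.

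**Concealment.** Setting last known alive to the day before death might look like concealment of the conflict. It is a derived value. The source dates remain in the database, which is subject to edit checks (SAP Section 8.2). The fair criticism is only that the derivation itself raises no flag.

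**Safeguards and materiality.** Protocol Section 8.4.7 asks for the date of death, Section 7.4 adds a search of public records for subjects lost to follow-up, and Section 8.4.9.1.3 requires fatal events that the investigator learns of in long-term follow-up to be reported within 24 hours. Partial dates may be few. No hypothesis is tested, and the dose recommendation rests on DLT rates. For PFS the death date matters only without earlier progression, and new therapy or missed assessments may censor first (SAP Appendix C). All of this stands, and it limits the size of the issue without closing the gap in the rule.

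**Conclusion.** The point holds in a limited form. Followed literally, item 2 can date a month-known death up to about 30 days before the subject was documented alive. It shortens OS, and PFS where death is the event, by at most about 1 month per affected subject, and it can cross the 6-month landmark. This rests on an alive date from a source that is not a patient visit or assessment; where the last visit is also the last alive date there is no error. The dates used above are assumed, and the number of partial death dates is not given. The expected effect on a descriptive secondary endpoint is small. Because SAP Table 7 reports OS by planned dose level, one subject weighs more there than in a pooled estimate.

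The second part is a gap in the specification: a confirmed death with only a year or no date has no stated OS treatment. The documents do not support calling it a rule that loses deaths.

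**What to change.** **Month-known deaths.** In item 2, replace the last contact date with the latest actual, non-imputed date among the Section 5 alive sources, computed without the death record. Impute the later of that date plus 1 day and the first of the death month. The non-imputed condition is needed because Appendix A moves partial medication stop dates to month end. The without-death condition is needed because Section 5 otherwise derives the alive date from the death date. If the alive date is the last day of the death month, use that day so that the result stays in the recorded month. Keep the existing data-error branch, and raise a query when an alive date falls after the recorded death month.

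**Year-only or undated deaths.** State before database lock how a confirmed death of this kind enters OS, and report a sensitivity analysis under an alternative treatment. No particular date is recommended here: 1 January of the death year, or the day after the last alive date, could be almost a year early. That is far more than the error being corrected.

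**Cost.** A few lines of SAP text, minor programming and possibly a few data queries. No new data collection is needed.
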